More recently, a micropulse delivery mode of diode laser (Micropulse TSCPC, mTSCPC) has been used to treat glaucoma by ablating the ciliary processes and reduce aqueous humor production with more selective targeting and less collateral damage.¹³ In contrast to conventional laser delivery where a continuous flow of high intensity energy is delivered, micropulse laser application delivers a series of repetitive short pulses of energy with rest periods in between pulses. This allows energy to build up in the targeted pigmented tissues, eventually reaching the coagulative threshold, while the adjacent non-pigmented structures have time to cool off during the off cycle without reaching the point of coagulation.²⁰⁻²⁷

Only a few studies have described the outcomes of this novel glaucoma therapy, showing mTSCPC to have comparable efficacy with fewer side effects when compared with traditional continuous wave mode diode laser delivery.^{13-14,28} This improved side effect profile has the potential to make mTSCPC an earlier therapeutic option instead of reserving it exclusively for end-stage refractory eyes.

Purpose

The goal of this study is to evaluate the efficacy and safety of the novel form of trans-scleral cyclophotocoagulation using micropulse diode laser and trans-pars plana treatment (Micropulse TSCPC, mTSCPC MP3, IRIDEX CYCLO G6[™] Glaucoma Laser System, CA, USA).

The main outcome will be the efficacy of the mTSCPC MP3 evaluated by the short-term and long-term reduction of IOP and number of anti-glaucomatous drops used postoperatively. The other outcomes will be the safety of this device by looking at the possible decrease in corrected distance visual acuity (CDVA), the progression of the optic nerve cupping and the complications.

Study Design

This will be a prospective, interventional and monocentric study based in a university hospital setting.

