The following baseline parameters will be recorded for each patient: age, gender, race/ethnicity, type of glaucoma diagnosis, ocular history (previous surgery and laser therapy), preoperative IOP, number of glaucoma medications prior to intervention, preoperative corrected distance visual acuity (CDVA), preoperative cup-to-disc ratio (CDR), pain level (using a verbal analog scale, see Table 3).

Table 3: Verbal analog scale for pain level	
Pain grade	Description of pain during laser, after subconjunctival anesthesia
None	No subjective feeling of pain.
Mild	Pain easily tolerable.
Moderate	Pain tolerable with difficulty.
Severe	Pain intolerable.

Treatment

The intervention will have to take place within thirty days following the screening appointment and will be executed by one of the two glaucoma specialists listed as the investigators of this study. The procedure will be done under local subconjunctival or rarely retrobulbar anesthesia.

All participants will have a treatment session of micropulse trans-scleral cyclophotocoagulation in the affected eye, using the MicroPulse[®] P3 Glaucoma Device (MP3) powered by the CYCLO G6[™] Glaucoma Laser System (Iridex, Mountain View, CA, USA).

Laser settings will be programmed as follows: power—2000mW-2500mW (average 2000mW) of 810nm infrared diode laser set on micropulse delivery mode; micropulse "on" time—0.5ms; micropulse "off" time—1.1ms; and duty cycle (proportion of each cycle during which the laser is on)—31.33 %.

The laser probe will be applied in a continuous sliding or painting motion from 9:30 to 2:30 and from 3:30 to 8:30. The 3 and 9 o'clock positions will be bypassed to avoid damage to ciliary neurovascular structures, as is standard technique with traditional continuous wave TSCPC. The probe will be applied perpendicular to the limbus with the edge directly on the limbus at all times (fiberoptic tip at 3 mm posterior to the limbus).

The laser will be delivered over 360° for 160–320s. Treatment duration will be adjusted based on iris color and glaucoma severity (mild glaucoma: 160s, moderate glaucoma: 240s, advanced glaucoma: 240-320s).

Post-Intervention Follow-Up

The patients will be seen by their attending ophthalmologist one (1) week, one (1) month, three (3) months, six (6) months, twelve (12) months and eighteen (18) months after the intervention. They will be seen more often if any complication occurs, in which case the frequency of their visits will be decided by their glaucoma specialist.

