
The following follow-up parameters will be recorded at each visit: postoperative IOP, number of glaucoma medications, corrected distance visual acuity (CDVA), cup-to-disc ratio (CDR), and presence of complications detected by a complete slit-lamp biomicroscopy examination. The pain level (using a verbal analog scale, see Table 3) will be assessed while performing the laser treatment.

A less than 25% reduction in IOP from baseline after 1 month on two consecutive visits separated by an interval of 1 week will be the basis for a second treatment. The same criteria will apply for third treatment if necessary. Repeat treatments will be done in the same conditions and settings as the primary treatment.

Primary and Secondary Outcomes

The primary outcome measure of success of this study will be defined as an IOP between 6 and 21 mmHg at final follow-up (18 months) with or without IOP lowering medications, at least 25% reduction in IOP at final follow-up compared to baseline, and no need for incisional glaucoma surgery during follow-up period. The need for a repeat micropulse TSCPC will not be considered a failure.

The secondary outcome measure of success will include the number of repeat treatments, the number of IOP lowering medications at 18 months, changes in CDVA (number of lines reduction or improvement from baseline), the progression of CDR compared to baseline, and the frequency of complications associated with the laser therapy (e.g., prolonged AC inflammation [cells 1+ or higher for more than 2 weeks with topical steroid eye drops], sympathetic ophthalmia, chronic hypotony, phthisis bulbi, scleral thinning).

The outcome of the therapy will ultimately be defined in terms of success rate, hypotony rates, response rates (success and hypotony rates considered together) and retreatment rates.

Statistical Analysis

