Paired 2-tailed Student t-tests will be used to compare changes in IOP, number of glaucoma medications, CDVA and CDR between each time point. For each of these measures, a single factor analysis of variance will be realized. Snellen visual acuities will be converted to logarithm of the minimum angle of resolution (logMAR) values for statistical analysis. Bonferroni correction will be used to control the multiplicity of t-tests. Frequency distribution and percentage will be used for categorical data. Demographic analysis will use Wilcoxon rank-sum test for age and chi-square test for gender. Fisher's exact test will evaluate equivalence of glaucoma types. A level of $p \le 0.05$ will be considered statistically significant. Analysis will be done with the SPSS version 20.0 software (SPSS Inc., Chicago, IL, USA).

Benefits, Risks and Disadvantages

Benefits

Micropulse trans-scleral CPC is thought to be an effective strategy to reduce the intraocular pressure in patients who are poor candidates for additional filtering surgery or implantation of glaucoma drainage devices. This therapy is considered less invasive and associated with fewer side effects than the traditional trans-scleral CPC procedure.

By participating in this study, patients will contribute to the research community in the ophthalmology field. The results already published on the micropulse trans-scleral CPC are encouraging, but additional results regarding the efficacy and safety of this procedure will further support its beneficial use.

Risks

Participants are exposed to all conventional complications that may be associated with CPC: prolonged anterior chamber inflammation, sympathetic ophthalmia, chronic hypotony, phthisis bulbi, scleral thinning, decrease in visual acuity, pain. However, the side effect profile of micropulse CPC is thought to be better than conventional glaucoma surgeries and conventional CPC, which has been used for many years in the treatment of advanced glaucoma. In case of failure of micropulse CPC to control adequately the IOP, there is always a possibility to add topical or systemic medication, or to undergo another surgery if needed.

Disadvantages

The only disadvantage in participating in this study will be to come to the requested follow-up appointments, which do not imply any risky or painful procedure.

Confidentiality

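### The paired t-tests are placed under Bonferroni without stating the contrasts, divisor or family; read literally, 15 of 21 pairs per measure serve no stated outcome and cost power, and the single-factor ANOVA is not stated to be within-patient

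*Combined protocol and SAP*

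**What the plan says.** In the combined protocol and SAP, the Statistical Analysis section states: "Paired 2-tailed Student t-tests will be used to compare changes in IOP, number of glaucoma medications, CDVA and CDR between each time point". It then adds "For each of these measures, a single factor analysis of variance will be realized" and "Bonferroni correction will be used to control the multiplicity of t-tests". Significance is set at 0.05. No list of pairs, number of tests or family is given.

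Under Post-Intervention Follow-Up, visits take place "one (1) week, one (1) month, three (3) months, six (6) months, twelve (12) months and eighteen (18) months after the intervention". With the preoperative values listed under Baseline Parameters, this makes seven time points, and all four measures are recorded at each of them.

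Primary and Secondary Outcomes refers the IOP component of success to baseline, counts medications at month 18, and lists "changes in CDVA (number of lines reduction or improvement from baseline), the progression of CDR compared to baseline". The Purpose section describes efficacy as a short-term and long-term reduction in IOP and drops. It names CDVA loss, together with "the progression of the optic nerve cupping and the complications", as safety outcomes.

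**The concern.** Under Bonferroni, every test added to the family tightens the threshold for all the others. If the family contains pairs that answer no stated question, the contrasts that do matter lose power for nothing. For CDVA and CDR, which the Purpose section treats as safety outcomes, the loss makes a true decline harder to declare. Because the contrasts and divisor are open, two analysts following the same text could also reach different verdicts on the same data.

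The ANOVA raises a separate question. Each patient contributes up to seven correlated values per measure. An ordinary one-way analysis would treat them as independent and leave the variation between patients in the error term.

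**Working it through.** **Inputs from the document.** Time points: 1 baseline + 6 visits = 7. Measures: 4. Patients: 50 (Population). Two-sided alpha: 0.05. The plan gives no power, SD, expected change or dropout, so it has no figure to reproduce. Every effect size, correlation and missingness rate below is an assumption.

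**Counting pairs.** 7 × 6 / 2 = 21 pairs per measure. Six include baseline and 21 − 6 = 15 do not. Over four measures: 4 × 21 = 84 and 4 × 6 = 24.

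**Thresholds.** 0.05/6 = 0.00833; 0.05/21 = 0.00238; 0.05/24 = 0.00208; 0.05/84 = 0.000595. The all-pairs reading is 21/6 = 3.5 times stricter, whichever family is used.

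**Power.** For a paired t-test with n = 50, let d be the mean change divided by the SD of change. Power is the probability that a noncentral t with 49 degrees of freedom and noncentrality d√50 exceeds the critical value, which is 2.750 for divisor 6 and 3.205 for divisor 21. At d = 0.4 the noncentrality is 2.828.

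| Assumed d | Uncorrected | Divisor 6 | Divisor 21 | Loss, 6 to 21 (points) |
|---|---|---|---|---|
| 0.2 | 28.3% | 10.1% | 4.6% | 5.6 |
| 0.3 | 54.8% | 27.7% | 15.5% | 12.2 |
| 0.4 | 79.2% | 53.6% | 36.6% | 17.0 |
| 0.5 | 93.4% | 78.0% | 63.0% | 15.0 |
| 0.6 | 98.6% | 92.7% | 84.2% | 8.5 |
| 0.8 | 100% | 99.8% | 99.1% | 0.7 |

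(Losses are taken before rounding.) The loss peaks at about 17 points near d = 0.42. The change detectable with 80% power rises from 0.510 to 0.576 SD. With an assumed 40 evaluable patients it rises from 0.576 to 0.652 SD. If the family spans all four measures, the detectable change is 0.583 SD with 24 tests and 0.643 SD with 84.

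**Other readings of the contrasts.**
- Each visit against baseline: 6 tests, no surplus pairs, no loss.
- Consecutive visits only: 6 tests, of which one (baseline to week 1) includes baseline. Baseline to month 18 is then never tested.

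**ANOVA.** Simulated with 50 patients and seven time points.
- No true change, nominal 0.05: an ordinary one-way ANOVA rejected in 0 to 0.0005 of runs under equal correlation of 0.5 to 0.9. It rejected in 0.0003 to 0.010 of runs when correlation decays with visit order or calendar time.
- Drift reaching 0.4 SD of change at month 18: one-way power was 26%, 2%, 57% and 20% (equal correlation 0.5, equal 0.7, first-order autoregressive 0.7, calendar decay to 0.5 at 18 months). Repeated-measures ANOVA with Greenhouse-Geisser correction gave 79%, 78%, 77% and 76%.

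**Complete cases.** If 5% or 10% of patients miss each visit independently, 50 × 0.95⁶ = 36.8 or 50 × 0.90⁶ = 26.6 have all six. A repeated-measures ANOVA with listwise deletion then has roughly 60% or 43 to 48% power for the same drift.

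**The case against.** The section never says that every pair is tested. A reader might infer that 21 tests per measure are fixed by the plan. That is the most literal reading but not the only one, and the loss exists only on that reading. This objection stands. The firm defect is that the contrasts, divisor and family are undefined.

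Comparing an early with a late visit could help to show whether an IOP reduction lasts, and the Purpose section does mention short-term and long-term reduction. But a reduction is a change from the preoperative value, so the outcomes can be met by baseline contrasts alone. Follow-up comparisons can be descriptive.

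Most of the fall from 79% to 37% at 0.4 SD (26 of 42 points) is the price of divisor 6, which is a legitimate choice. Only 17 points belong to the surplus pairs, and 0.4 SD lies close to the worst case. This stands too.

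A reader might also infer that the correction will be used to present the device as safe. The document does not support that. Nothing says that non-significance will be reported as safety, and the section on outcomes closes with "The outcome of the therapy will ultimately be defined in terms of success rate, hypotony rates, response rates" and retreatment rates, none of which is a t-test on CDVA or CDR. Correcting these two measures, which are also listed as secondary measures of success, is a defensible conservative choice.

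Finally, a single factor could mean time as a within-patient factor. The text neither says nor excludes this, so one clarifying phrase is needed. The paired t-tests do not depend on the ANOVA, and their standard errors are valid either way.

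**Conclusion.** The concern holds as a minor point. The contrasts, divisor and Bonferroni family are not defined. On the literal all-pairs reading with a per-measure family, 15 pairs that no outcome requires cost 5.6, 12, 17, 15, 8.5 and under 1 points of power at assumed changes of 0.2, 0.3, 0.4, 0.5, 0.6 and 0.8 SD with 50 patients. On the visit-versus-baseline reading there is no loss. On the consecutive-visit reading the month-18 change from baseline goes untested. The same wording repairs all three.

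The ANOVA would be very conservative (type I error about 0 to 0.01) if run as an ordinary one-way analysis. The document does not establish that it will be, and the effect is confined to the omnibus test.

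The binary primary outcome and the complication frequencies are untouched, and changes of about 0.8 SD are detected under either divisor.

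**What to change.** Change analysis wording only:

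1. Limit the paired t-tests to the six visit-minus-baseline contrasts per measure, name month 18 as the main contrast, and state Bonferroni with divisor 6 within each measure. Treat any comparison between follow-up visits as descriptive and outside the family.
2. Replace the single-factor ANOVA with a mixed model for repeated measures: visit as a categorical effect, unstructured within-patient covariance, all available visits used. If a repeated-measures ANOVA with Greenhouse-Geisser correction is preferred, state that listwise deletion reduces the sample (to about 37 or 27 of 50 under the assumed missingness) and give the resulting power.
3. Report CDVA and CDR changes from baseline with 95% confidence intervals alongside the corrected tests, and state that non-significance is not evidence of safety. With 50 patients an unadjusted interval extends 2.010/√50 = 0.284 SD of change either side.

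Dropping the correction for CDVA and CDR is optional and a trade-off. Over 12 unadjusted contrasts about 12 × 0.05 = 0.6 false signals are expected. If nothing changes and the two measures are independent, the chance of at least one is about 30 to 38%.

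The cost is the loss of formal tests between follow-up visits and slightly more analysis work; no new data or visits are needed. The mixed model mainly provides a valid omnibus test. In simulation with 5% or 10% missed visits, it gained only 0 to 5 points of power over the paired t-test at month 18.

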Based on the established inclusion and exclusion criteria, the study investigators will enrol patients followed in their own clinic or new patients referred by other ophthalmologists. After learning and asking questions about the risks and benefits of participating in this study, patients will be requested to sign the appropriate information and consent form. They will then have a complete pre-interventional ophthalmologic evaluation including corrected distance visual acuity (CDVA), a complete slit-lamp biomicroscopy examination, an IOP measurement with the Goldmann applanation tonometer, a measurement of the central corneal thickness with a handheld pachymeter (IOPac Advanced, Heidelberg Engineering, Franklin, MA, USA), and a dilated fundus examination with a particular attention to the cup-to-disk ratio (CDR) of the optic nerve.

Population

A total of fifty (50) glaucoma patients will be included in this prospective study. They will be recruited by two (2) glaucoma specialists at the Notre-Dame Hospital department of ophthalmology (University of Montreal Hospital Center, CHUM). Patients will meet the inclusion and exclusion criteria listed below (Tables 1-2). Participants will undergo a micropulse transscleral cyclophotocoagulation (mTSCPC MP3) treatment session in the affected eye.

Table 1: Inclusion criteria
Patients of either sex and any race aged 18 years old and above.
Followed by a glaucoma subspecialist at University of Montreal Hospital Center.
IOP above target and unresponsive to maximal tolerated medical therapy with or without
previous surgical intervention.
a. mild glaucoma: IOP > 18 mmHg
 b. moderate glaucoma: IOP > 15 mmHg
c. advanced glaucoma: IOP > 12 mmHg
Considered poor candidates for additional filtering surgery or implantation of glaucoma
drainage devices.

Table 2: Exclusion criteria

Patients unable to give informed consent.

Patients with significant scleral thinning, defined as thinning of more than one clock hour noticed on scleral transillumination.

Ocular infection or inflammation in the study eye in the 2 months prior to enrolment. Intraocular surgery in the study eye in the 2 months prior to enrolment.

Baseline Parameters

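### Cheap improvement, not an error: Holm's step-down procedure could replace single-step Bonferroni for the paired t-tests, with the same error control and never fewer rejections

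*Combined protocol and SAP*

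**What the plan says.** Under Statistical Analysis the combined protocol and SAP sets out the tests: "Paired 2-tailed Student t-tests will be used to compare changes in IOP, number of glaucoma medications, CDVA and CDR between each time point". It then says "Bonferroni correction will be used to control the multiplicity of t-tests" and "A level of $p \le 0.05$ will be considered statistically significant". No step-down version is named, no adjusted threshold is given, and no confidence intervals are planned.

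The section does not say how many tests form the family, or whether the correction runs within each measure or across all four. The follow-up schedule has visits at "one (1) week, one (1) month, three (3) months, six (6) months, twelve (12) months and eighteen (18) months after the intervention", so with baseline there are seven time points. On size, the Population section says "A total of fifty (50) glaucoma patients will be included in this prospective study", with no power calculation.

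The primary outcome, under Primary and Secondary Outcomes, is a yes/no composite of success at 18 months. It is not among the measures listed for t-tests. CDVA and CDR are safety outcomes under Purpose and also appear among the secondary outcomes.

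**The concern.** Single-step Bonferroni holds every test to 0.05/m, however many of the others have already been rejected. Holm's procedure starts at the same threshold and relaxes it after each rejection. It needs no further assumption and controls the same error rate.

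The usual reason to keep Bonferroni is that it comes with simple matching simultaneous intervals, and this plan does not use them. With 50 patients, power for modest changes is limited under any of the possible families, so giving some away deserves a second look.

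**Working it through.** **Inputs from the document.** Alpha 0.05, two-sided paired t-tests, four measures, seven time points, n = 50. The plan states no power, effect size or SD, so there is no figure of its own to reproduce.

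**Possible families.** Against baseline: 6 tests per measure, 6 × 4 = 24 pooled. All pairs: 7 × 6 / 2 = 21 per measure, 21 × 4 = 84 pooled.

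**Bonferroni is valid.** Thresholds are 0.05/6 = 0.00833, 0.05/21 = 0.00238, 0.05/24 = 0.00208 and 0.05/84 = 0.000595. For independent tests the family-wise error, 1 − (1 − 0.05/m)^m, is about 4.9% in each case.

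**Holm gives the same control and never fewer rejections.** Order the p-values and compare the k-th smallest with 0.05/(m − k + 1), stopping at the first failure. Every threshold is at least 0.05/m, so any test that Bonferroni rejects, Holm rejects. With m0 true nulls, the first false rejection must come at a step whose threshold is at most 0.05/m0, so the family-wise error is at most m0 × 0.05/m0 = 5% under any dependence.

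**Exact Bonferroni power.** Noncentral t, df 49, noncentrality d√50. At d = 0.4: 79% uncorrected, 53.6% (m = 6), 36.6% (m = 21), 35.0% (m = 24), 22.0% (m = 84).

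**One step of Holm by hand, d = 0.4.**
- Pooled family of 24: if the 12 IOP and medication contrasts are rejected, the next divisor is 24 − 12 = 12, and power rises from 35.0% to 43.8%. With n = 40 it rises from 24.2% to 32.0%.
- Pooled family of 84: if the same 12 baseline contrasts are rejected, the next divisor is 84 − 12 = 72, and power rises from 22.0% to 23.4%.

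**Full Holm by simulation.** Assumptions: n = 50 with complete data; correlation 0.5 between time points within a measure; measures independent; a constant shift after baseline; standardised paired changes of IOP 1.2, medications 1.0, CDVA 0.4, CDR 0.4 unless noted. The table gives average power for a CDVA baseline contrast, Bonferroni to Holm, from two separate runs.

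| Family | 20,000 trials | 3,000 trials |
|---|---|---|
| 24 pooled, against baseline | 35.0% to 54.9% | 35.7% to 56.0% |
| 24 pooled, CDR null | 34.7% to 46.7% | 35.1% to 47.7% |
| 6 per measure, against baseline | 53.5% to 64.4% | 54.8% to 66.2% |
| 84 pooled, all pairs | 21.9% to 23.7% | 21.9% to 23.9% |
| 21 per measure, all pairs | 36.5% to 37.9% | 36.3% to 37.6% |

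In neither run did Bonferroni reject a test that Holm did not. The full procedure gains more than the single hand step because rejections among CDVA and CDR tests shrink the divisor further. The all-pairs gain is small because, with a steady effect, tests between post-treatment visits are null and keep the divisor large.

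**Sensitivity (3,000-trial run).** With IOP and medications at 0.5 and a pooled family of 24, all four measures gain: IOP 61.6% to 72.1%, medications 61.3% to 71.4%, CDVA 34.5% to 47.0%, CDR 35.1% to 47.3%. With IOP and medications at 1.2 and 1.0 but CDVA and CDR at 0.2, CDVA power is low either way: 4.4% to 7.2% (24 pooled) and 1.8% to 2.1% (84 pooled).

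**The case against.** Bonferroni is conventional, does what the plan asks of it, and makes no conclusion invalid. The same remark could be made of any plan that names it. That stands: this is a matter of efficiency only.

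The missing definition of the family also matters more than the choice of procedure on the all-pairs reading. At d = 0.4, moving from 6 to 84 tests takes Bonferroni power from 54% to 22%, whereas Holm adds 1 to 2 points there. That stands too. It bears on the size of the gain, not on its direction.

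A reader might infer two stronger things that the documents do not support.
- **That the loss falls chiefly on CDVA and CDR, so that harm would be missed.** This needs IOP and medication effects so large that their power is already near 100%, and the documents give no effect sizes. For alpha to pass between measures it also needs one pooled family, which the plan does not specify. With moderate IOP and medication effects all four measures gain, and with small CDVA and CDR effects Holm does not rescue the signal. Safety also rests on complication frequencies and counts of acuity lines, not only on these p-values.
- **That the gain is also large on the literal all-pairs reading.** Halving the divisor from 84 to 42 would lift power from 22.0% to 28.7% at d = 0.4. It would require all 42 IOP and medication pairs to be significant, including the 30 between post-treatment visits (15 per measure). Large changes from baseline do not imply that.

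Finally, Holm has no equally simple simultaneous intervals. This is a real but modest cost, since the plan specifies none.

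**Conclusion.** The point holds as an optional, nearly costless improvement. That Holm rejects at least as often with the same error control is true for every family the plan might intend, and needs no assumption about effects.

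The size of the gain does rest on assumptions: the effects, correlation and complete data listed above. For a CDVA change of 0.4 SD it is about 20 points with 24 pooled baseline contrasts (about 12 if CDR is null), about 11 with six baseline tests per measure, and 1 to 2 if all pairs are tested. The primary success outcome is not affected.

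**What to change.** Replace the Bonferroni sentence with: *Holm's step-down procedure will be used to control the family-wise error of the t-tests at 5%.* Apply it to whatever family the plan intends and state that family in the same place, since the new sentence does not define it. Report Holm-adjusted p-values beside ordinary 95% confidence intervals.

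The cost is one sentence and sorting the p-values, with no new data or patients. The intervals will be unadjusted, so one may occasionally exclude zero where the Holm-adjusted p-value exceeds 0.05. The report should say so.
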